10.3.5. Reporting of SAEs

SAE Reporting via an Electronic Data Collection Tool

- The primary mechanism for reporting an SAE will be the electronic data collection tool.
- If the electronic system is unavailable, then the site will use the SAE paper form (see next section) in order to report the event within 24 hours.
- The site will enter the SAE data into the electronic system as soon as it becomes available.
- After the study is completed at a given site, the electronic data collection tool will be taken off-line to prevent the entry of new data or changes to existing data.
- If a site receives a report of a new SAE from a study participant or receives updated data on a previously reported SAE after the electronic data collection tool has been taken off-line, then the site can report this information on a SAE paper form (see next section) or to the medical monitor/SAE coordinator by telephone.
- Contacts for SAE reporting can be found in the SAE paper form.

SAE Reporting via Paper Form

• Facsimile transmission of the SAE paper form is the preferred method to transmit this information to the medical monitor or the SAE coordinator.

- Initial notification via telephone does not replace the need for the investigator to complete and sign the SAE CRF pages within the designated reporting time frames.
- Contacts for SAE reporting can be found in the SAE paper form.

10.3.6. Regulatory Reporting Requirements

SAE Regulatory Reporting

- Prompt notification by the investigator to the sponsor of a SAE is essential so that legal obligations and ethical responsibilities towards the safety of participants and the safety of a study intervention under clinical investigation are met.
- The sponsor has a legal responsibility to notify both the local regulatory authority and other regulatory agencies about the safety of a study intervention under clinical investigation. The sponsor will comply with country-specific regulatory requirements relating to safety reporting to the regulatory authority, IRB/IEC, and investigators.
- An investigator who receives an investigator safety report describing a SAE or other specific safety information (for example, summary or listing of SAEs) from the sponsor will review and then file it along with the IB or state other documents and will notify the IRB/IEC, if appropriate according to local requirements.

10.4. Appendix 4: Contraceptive and Barrier Guidance

10.4.1. Definitions

Word/Phrase	Definition
Women of childbearing potential (WOCBP)	Adult females are considered WOCBP unless they are WNOCBP.
Women not of childbearing potential (WNOCBP)	Females are considered WNOCBP if they • have a congenital anomaly such as Müllerian agenesis • are infertile due to surgical sterilization, or • are postmenopausal. Examples of surgical sterilization include total hysterectomy, bilateral salpingo-oophorectomy, bilateral salpingectomy, or bilateral oophorectomy.
Postmenopausal state	 at any age at least 6 weeks post-surgical bilateral oophorectomy with or without hysterectomy, confirmed by operative or medical note; or aged at least 40 years and up to 55 years with an intact uterus, not on hormone therapy^a, who has had cessation of menses for at least 12 consecutive months without an alternative medical cause, AND with a follicle-stimulating hormone >40 mIU/mL; or 55 years or older not on hormone therapy, who has had at least 12 months of spontaneous amenorrhea, or aged at least 55 years with a diagnosis of menopause prior to starting hormone replacement therapy. a Women should not be taking medications during amenorrhea such as oral contraceptives, hormones, gonadotropin-releasing hormone, anti-estrogens, SERMs, or chemotherapy that could induce transient amenorrhea.

10.4.2. Contraception Guidance

Contraception methods should be aligned with local regulations for both male and female participants.

WOCBP who are completely abstinent as their preferred and usual lifestyle, or in a same-sex relationship as their preferred and usual lifestyle:

relationship as their pre	sterred and asaar mestyle:
Must	Must not
agree to either	use periodic abstinence methods
remain abstinent or	o calendar
stay in a same-sex	o ovulation
relationship without	o symptothermal, or
sexual relationships	o post-ovulation
with males	declare abstinence just for the duration of a trial, or

WOCBP who are NOT completely abstinent as their preferred and usual lifestyle, or NOT in a same-sex relationship as their preferred and usual lifestyle, must do the following:

Topic	Condition
Pregnancy testing	Have a negative serum test result at screening followed by a negative
	urine result within 24 hours prior to treatment exposure. See the protocol
	SoA for subsequent pregnancy testing requirements.
Contraception	Agree to use 2 forms of effective contraception, where at least 1 form must be highly effective.
	These forms of contraception must be used during the study and after the study for at least 95 days after the last dose of the study intervention.

Examples of different forms of contraception:

Examples of different forms of contraception:		
Methods	Examples	
Highly effective contraception (less than 1% failure rate)	 female sterilization combination oral contraceptive pill progestin-only contraceptive pill (mini-pill) implanted contraceptives injectable contraceptives contraceptive patch (only women <198 pounds or 90 kg) total abstinence vasectomy (if only sexual partner) fallopian tube implants (if confirmed by 	
	hysterosalpingogram) • combined contraceptive vaginal ring, or • intrauterine devices	
Effective contraception	 male or female condoms with spermicide diaphragms with spermicide or cervical sponges barrier method with use of a spermicide condom with spermicide diaphragm with spermicide, or female condom with spermicide 	
	Note: The barrier method must include use of a spermicide (that is, condom with spermicide, diaphragm with spermicide, or female condom with spermicide) to be considered effective.	
Ineffective forms of contraception whether used alone or in any combination	 spermicide alone periodic abstinence fertility awareness (calendar method, temperature method, cervical mucus, or symptothermal) withdrawal postcoital douche, or lactational amenorrhea 	

The tables below describes contraception guidance for men.

Topic	Guidance
For all men	Should refrain from sperm donation for the duration of the study and for the predicted time until estimated plasma levels of partner would be below the level of toxicologic concern, plus 90 days
Contraception for men with partners of childbearing potential	 either remain abstinent (if this is their preferred and usual lifestyle), or must use condoms during intercourse for the duration of the study, and for the predicted time until estimated plasma levels of partner would be below the level of toxicologic concern, plus 90 days
Contraception for men in exclusively same-sex relationships, as their preferred and usual lifestyle	Are not required to use contraception

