 - a. Males who agree to use highly effective or effective methods of contraception may participate in this trial. Please refer to Appendix 10.4 for definitions and additional guidance related to contraception.
 - b. Women of childbearing potential (WOCBP) who agree to use highly effective or effective methods of contraception and women not of childbearing potential (WNOCBP) may participate in this trial. See Appendix 10.4 for definitions and additional requirements related to contraception.

Contraceptive use by participants should be consistent with local regulations regarding the methods of contraception for those participating in clinical studies. For the contraception requirements of this protocol, see Appendix 10.4.

Informed Consent

7. Capable of giving signed informed consent as described in Appendix 10.1, which includes compliance with the requirements and restrictions listed in the ICF and in this protocol.

Other Inclusions

8. Are reliable and willing to make themselves available for the duration of the study and are willing to follow study procedures, including willing and able to take four 12-mm round concave tablets of study drug every day for 12 weeks, in the opinion of the investigator.

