8.3.1. Timing and Mechanism for Collecting Events

This table describes the timing, deadlines, and mechanism for collecting events.

Event	Collection	Collection	Timing for Reporting	Mechanism for	Back-up
Event	Start	Stop	to Sponsor or Designee	Reporting	Method of Reporting
Adverse Event					
AE	Signing of the ICF	Participation in study has ended	As soon as possible upon site awareness	AE CRF	N/A
AE – related to prescreening study procedure	Signing of the prescreening ICF	Signing of the ICF	As soon as possible upon site awareness	AE CRF	N/A
Serious Adverse	Event				
SAE and SAE updates – prior to start of study intervention and deemed reasonably possibly related to study procedures	Signing of the ICF	Start of intervention	Within 24 hours of awareness	SAE CRF	SAE paper form
SAE and SAE updates – after start of study intervention	Start of intervention	Participation in study has ended	Within 24 hours of awareness	SAE CRF	SAE paper form
SAE ^a – after participant's study participation has ended and the investigator becomes aware	After participant's study participation has ended	N/A	Promptly	SAE paper form	N/A

Event	Collection Start	Collection Stop	Timing for Reporting to Sponsor or Designee	Mechanism for Reporting	Back-up Method of Reporting
Pregnancy					
Pregnancy in female participants and female partners of male participants	After the start of study intervention	At least 65 days after the last dose of study intervention	Within 24 hours (see Section 8.3.2)	Pregnancy paper form	Pregnancy paper form
Product Complain	ints				
PC associated with an SAE or might have led to an SAE	Start of study intervention	End of study intervention	Within 24 hours of awareness	PC form	N/A
PC not associated with an SAE	Start of study intervention	End of study intervention	Within 1 business day of awareness	PC form	N/A
Updated PC information	_		As soon as possible upon site awareness	Originally completed PC form with all changes signed and dated by the investigator	N/A
PC, if investigator becomes aware	Participation in study has ended	N/A	Promptly	PC form	

Abbreviations: AE = adverse event; CRF = case report form; ICF = informed consent form; N/A = not applicable; PC = product complaint; SAE = serious adverse event.

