8.3.2. Pregnancy

Collection of pregnancy information

Male participants with partners who become pregnant

• The investigator will attempt to collect pregnancy information on any male participant's female partner who becomes pregnant while the male participant is in this study. This applies only to male participants who receive study intervention.

^a SAEs should not be reported unless the investigator deems them to be possibly related to study treatment or study participation.

• After learning of a pregnancy in the female partner of a study participant, the investigator will

- obtain a consent to release information from the pregnant female partner directly, and
- o within 24 hours after obtaining this consent will record pregnancy information on the appropriate form and submit it to the sponsor.

The female partner will also be followed to determine the outcome of the pregnancy. Information on the status of the mother and child will be forwarded to the sponsor. Generally, the follow-up will be no longer than 6 to 8 weeks following the estimated delivery date. Any termination of the pregnancy will be reported regardless of gestational age, fetal status (presence or absence of anomalies), or indication for the procedure.

Female participants who become pregnant

- The investigator will collect pregnancy information on any female participant who becomes pregnant while participating in this study. The initial information will be recorded on the appropriate form and submitted to the sponsor within 24 hours of learning of a participant's pregnancy.
- The participant will be followed to determine the outcome of the pregnancy. The investigator will collect follow-up information on the participant and the neonate and the information will be forwarded to the sponsor. Generally, follow-up will not be required for longer than 6 to 8 weeks beyond the estimated delivery date. Any termination of pregnancy will be reported, regardless of gestational age, fetal status (presence or absence of anomalies), or indication for the procedure.
- While pregnancy itself is not considered to be an AE or SAE, any pregnancy complication or elective termination of a pregnancy for medical reasons will be reported as an AE or SAE.
- A spontaneous abortion (occurring at <20 weeks gestational age) or still birth (occurring at ≥20 weeks gestational age) is always considered to be an SAE and will be reported as such.

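### Pregnancy collection may stop 65 days after the last dose, before the required contraception period ends (at least day 95 for women; an unquantified time plus 90 days for men)

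*Protocol*

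**What the plan says.** **Entry condition.** Protocol Section 5.1, criterion 6a: "Males who agree to use highly effective or effective methods of contraception may participate in this trial". The closing sentence of criterion 6 sends the reader on: "For the contraception requirements of this protocol, see Appendix 10.4".

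**Contraception period, women.** Appendix 10.4.2 requires women of childbearing potential to whom the rules apply to continue contraception "after the study for at least 95 days after the last dose of the study intervention".

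**Contraception period, men.** The same appendix says that men with partners of childbearing potential, unless abstinent, "must use condoms during intercourse for the duration of the study", and then "for the predicted time until estimated plasma levels of partner would be below the level of toxicologic concern, plus 90 days". Sperm donation is restricted for the same period. Neither document gives a value for the predicted time.

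**Collection window.** One row of the table in Section 8.3.1 covers "Pregnancy in female participants and female partners of male participants". Its collection stop is "At least 65 days after the last dose of study intervention".

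**Procedure.** Section 8.3.2 describes how pregnancy information is gathered. For partners it speaks of a woman who "becomes pregnant while the male participant is in this study", and it uses similar in-study wording for female participants. After the study, it asks only for pregnancy-related serious adverse events that the investigator considers reasonably related, and it does not oblige the investigator to look for them.

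**The concern.** The collection window and the contraception period both run on after dosing, but they end on different days, and collection may end first. By setting a contraception period, the sponsor asks participants to avoid conception on a precautionary basis until a given time. If a conception occurs in that time despite the precaution, its outcome is the information the sponsor would want for an unapproved drug. Under the current text a site may close collection at day 65 and be fully compliant, although the participant is still under the contraception duty. At stake is the completeness of pregnancy and fetal safety data. No efficacy result is involved.

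The men's period adds a practical difficulty. Because it is not expressed in days, the collection stop for partners cannot be matched to it until the sponsor supplies a figure.

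**Working it through.** No derivation of the 65-day minimum is given, so there is no planned figure to reproduce. The check is a count of days from the last dose (day 0), by the day on which the pregnancy begins.

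**Inputs**
- Collection minimum, women and partners: day 65 (Section 8.3.1).
- Contraception minimum, women: day 95 (Appendix 10.4.2).
- Contraception, men: T + 90 days, where T is the predicted time and has no stated value (Appendix 10.4.2). The text does not say clearly whether the clock starts at the last dose or at the end of the study.
- Last visit (801): 4 weeks ± 5 days after the last dose, so day 23 to 33 (Section 1.3).

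**Formula:** gap = end of contraception period − collection minimum.

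**Female participants:** 95 − 65 = 30 days (days 66 to 95), or 30/95 = 32% of the period.

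**Partners of male participants**

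| Start of the men's clock | End of period | Gap beyond day 65 |
|---|---|---|
| Last dose | 90 + T | 25 + T |
| Visit 801 (day 23 to 33) | 113 to 123 + T | 48 to 58 + T |

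The lower bound of 25 days needs no assumption except T ≥ 0. As an illustration only, assuming T between 0 and 28 days, the gap is 25 to 53 days from the last dose, or 48 to 86 days from Visit 801.

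**Does another provision cover the gap?**
- The last scheduled pregnancy test is at Visit 801, by day 33.
- Section 10.3.2 classes abnormal pregnancy outcomes as serious adverse events, and Section 8.3.1 puts no end date on serious events learned of after participation. Its footnote limits these to events possibly related to treatment or participation.
- This route is passive and does not capture uncomplicated pregnancies or outcomes judged unrelated.

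**The case against.** **The two periods need not match.** The protocol never says that risk persists to day 95, and contraception rules are precautionary. Section 1.3 says that 4 weeks exceeds five effective half-lives, so the half-life is below 28/5 = 5.6 days and 65 days is more than 11 half-lives. The 65 days is also a minimum, so longer collection is allowed. This stands as far as it goes: the present text breaks no rule, and the point is an inexpensive improvement. It does not explain why collection should end while the sponsor's own precaution is still in force.

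**Serious outcomes have an open-ended route.** That is correct for related events. What remains uncovered is stated above.

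**Stronger readings that the documents do not support**
- *That collection really ends at Visit 801.* From the in-study wording of 8.3.2, a reader might infer gaps of 62 to 72 days for women (95 − 33, 95 − 23) and at least 57 to 67 days for partners (90 − 33, 90 − 23). Section 8.3.1 is the specific timing table and gives an explicit stop. It governs over the general wording of 8.3.2.
- *That the men's period can be filled in as 28 + 90 = 118 days from the last dose, or given a floor of 90 days.* The 28 days is washout in the participant and says nothing about the time to a partner's level of concern. If the clock starts at study end, the present text already runs to day 113 to 123 + T. A 90-day floor would lie below that for any T, and with T = 28 the 118-day figure would shorten the duty by 23 to 33 days.
- *That sites have no date to give men.* The protocol lacks the number, but the consent form and the Investigator's Brochure were not available and may contain it. The missing figure is by itself only missing detail.

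**Conclusion.** The concern holds as a mismatch between Section 8.3.1 and Appendix 10.4. Required collection ends 30 days before the women's contraception period and at least 25 days before the men's. The first figure rests only on stated minimums; the second also assumes that the predicted time is not negative. The full size of the men's gap cannot be determined, because both the predicted time and its start point are missing.

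Severity is minor. The documents do not allow a count of affected pregnancies. Few are likely, given the entry age and the sample size.

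**What to change.** 1. **Section 8.3.1:** set the pregnancy collection stop to at least 95 days after the last dose for female participants, and to the end of the men's contraception period for partners.
2. **Section 8.3.2:** replace the in-study wording with a reference to the 8.3.1 window.
3. **Appendix 10.4.2, men:** state the period as a number of days with its start point, taken from the sponsor's own partner-exposure estimate. This review proposes no figure.
4. **Visit 801:** tell participants to report any pregnancy up to the applicable date.

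**Cost.** A protocol amendment with ethics approval (and health-authority approval if it is classed as substantial), a consent-form update, and possibly one later telephone contact for participants to whom the contraception rules apply. Partner information already needs the partner's own consent under 8.3.2, and that would extend to the later pregnancies. No new visit or sample is needed.

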10.5. Appendix 5: Genetics

Use/Analysis of DNA

Genetic variation may impact a participant's response to study intervention, susceptibility to, and severity and progression of disease. Variable response to study intervention may be due to genetic determinants that impact drug absorption, distribution, metabolism, and excretion; mechanism of action of the drug; disease etiology; and/or molecular subtype of the disease being treated. Therefore, where local regulations and IRB/IEC allow, an optional blood sample will be collected for DNA analysis from consenting participants.

- DNA samples will be used for research related to study intervention or cardiovascular disease and related diseases. They may also be used to develop tests or assays including diagnostic tests related to study intervention and cardiovascular disease. Genetic research may consist of the analysis of 1 or more candidate genes or the analysis of genetic markers throughout the genome or analysis of the entire genome (as appropriate).
- The samples may be analyzed as part of a multi-study assessment of genetic factors involved in the response to study intervention or study interventions of this class to understand study disease or related conditions.
- The results of genetic analyses may be reported in the CSR or in a separate study summary.
- The sponsor will store the DNA samples in a secure storage space with adequate measures to protect confidentiality.
- The samples will be retained while research on study intervention continues but no longer than 7 years or other period as per local requirements.

10.6. Appendix 6: Liver Safety: Suggested Actions and Follow-up Assessments

Hepatic Evaluation Testing

See Section 8.2.3 for guidance on appropriate test selection.

The Lilly-designated central laboratory should complete the analysis of all selected testing except for testing listed in the investigator-designated local laboratory table. The central laboratory will report results if a validated test or calculation is available.

Local testing may be performed *in addition to central testing* when necessary for immediate participant management.

The local laboratory must be qualified in accordance with applicable local regulations.

Tests assayed by Lilly-designated central laboratory	
Hepatic Hematology Panel	Hepatitis A virus (HAV) testing:
Hemoglobin	HAV total antibody
Hematocrit	HAV IgM antibody
Erythrocytes (RBCs - red blood cells)	Hepatis B virus (HBV) testing:
Leukocytes (WBCs - white blood cells)	Hepatitis B surface antigen (HBsAg)
Differential:	Hepatitis B surface antibody (anti-HBs)
Neutrophils, segmented	Hepatitis B core total antibody (anti-HBc)
Lymphocytes	Hepatitis B core IgM antibody
Monocytes	HBV DNA b
Basophils	Hepatis C virus (HCV) testing:
Eosinophils	HCV antibody
Platelets	HCV RNA b
Cell morphology (RBC and WBC)	Hepatitis D virus (HDV) testing:
Hepatic Clinical Chemistry Panel	HDV antibody
Total bilirubin	Hepatitis E virus (HEV) testing:
Direct bilirubin	HEV IgG antibody
Alkaline phosphatase (ALP)	HEV IgM antibody
Alanine aminotransferase (ALT)	HEV RNA b
Aspartate aminotransferase (AST)	Anti-nuclear antibody (ANA)
Gamma-glutamyl transferase (GGT)	Anti-smooth muscle antibody (ASMA) a
Creatine kinase (CK)	Anti-actin antibody ^c
Hepatic Coagulation Panel	Immunoglobulin IgA (quantitative)
Prothrombin time, INR (PT-INR)	Immunoglobulin IgG (quantitative)
Urine Chemistry	Immunoglobulin IgM (quantitative)
Drug screen	Epstein-Barr virus (EBV) testing:
Haptoglobin	EBV antibody

Tests assayed ONLY by investigator-designated local laboratory	
Acetaminophen	Cytomegalovirus (CMV) testing:
Acetaminophen protein adducts	CMV antibody
Alkaline phosphatase isoenzymes	CMV DNA b
Ceruloplasmin	Herpes simplex virus (HSV) testing:
Copper	HSV (Type 1 and 2) antibody
Ethyl alcohol (EtOH)	HSV (Type 1 and 2) DNA b

Tests assayed ONLY by investigator-designated local laboratory	
Phosphatidylethanol (PEth)	Liver kidney microsomal type 1 (LKM-1) antibody
Urine Chemistry	Microbiology
Ethyl glucuronide (EtG)	Culture:
Epstein-Barr virus (EBV) testing:	Blood
EBV DNA b	Urine

- a Not required if anti-actin antibody is tested.
- b Reflex/confirmation dependent on regulatory requirements, testing availability, or both.
- ^c Not required if anti-smooth muscle antibody (ASMA) is tested.

